KAS-R. The KAS-R contains five major sections which focus on several dimensions of community and social adjustment as well as general psychological disturbances. Section R1 contains 127 questions concerned with psychiatric symptoms and social behavior. Sections R2 and R3 are concerned with the patient's performance of socially expected activities and the expectations that others have for his performance of these activities. Similarly, section RS4 deals with the level of free-time activities and section R5 covers the respondent's level of satisfaction with those.

The KAS-R takes about 30 minutes to administer to the patient's spouse or another person with whom the patient has a close relationship.

Because the KAS-R is completed by the patient's relative, it permits an independent measurement of the patient's functioning as well as a measure of how he is perceived by others. In the present study, the KAS-R will be administered to the patient's relative by the psychometrist at baseline and at twelve months following treatment.

In one study reported by Hogarty (1975), the median internal reliability for the five scales was found to be .725. Other studies (e.g., Katz and Lyerly, 1963) show similar high test-retest and internal consistency reliabilities.

The KAS-R has also been shown to be highly predictive of ratings of subject adjustment made by experienced psychologists and social workers (Hogarty, Ulrich and Katz, 1973), while other studies have demonstrated the effectiveness of the KAS in predicting the course of adjustment over time (Michaux et al., 1969) and in differentiating various patient populations (Hogarty et al., 1968). Although the scale has been used most frequently to assess the effectiveness of psychiatric treatment, the scales also have proven to be useful with psychiatrically normal populations (Hogarty and Katz, 1971).

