SIP. The SIP is a measure of health status developed for use as an outcome measure in the evaluation of medical care. Specifically, it is a questionnaire instrument designed to measure sickness-related behavioral dysfunction. It provides an overall dysfunction score, as well as separate dysfunction scores for fourteen categories or types of activity. The categories involve behaviors related to social interaction, ambulation, sleep and rest, taking nutrition, usual daily work, household management, mobility and confinement, movement of the body, communication activity, leisure pastimes and recreation, intellectual functioning, interaction with family members, emotions, feelings and sensations, and personal hygiene. It consists of 189 items and may be completed by the respondent in 20-30 minutes. Test-retest reliability coefficients for the overall score are on the order of .90 (Pollard et al., 1976). Construct validity has been examined using self-assessment and clinician assessment of health status and related function assessment procedures. The correlations obtained are on the order of .40 to .60 (Bergner et al.; 1976). The SIP will be administered to the patient at baseline and twelve months after baseline.

POMS. The POMS consists of a list of 65 adjectives that the patient rates on a five-point scale to indicate current mood. Subscales on the POMS include Tension-Anxiety, Depression-Dejection, Anger-Hostility, Vigor-Activity, Fatigue-Inertia and Confusion-Bewilderment.

The POMS is very brief; it takes about five to ten minutes to complete. Thus, it will be used as a repeated measure of mood.

The psychometric characteristics and utility of the POMS have also been examined in many studies (cf. McNair et al., 1971). In six studies the internal consistencies of the six factor-scales of the POMS have ranged from .84 to .95. Stability coefficients ranged from .65 to .74 for a 20 day test-retest interval and from .43 to .52 for a six-week interval.

The POMS has proven to be highly sensitive to emotion inducing conditions such as anxiety inducing films (Pillard et al., 1967) and psychotropic drugs (Lorr et al., 1964) and short-term psychotherapy programs (Lorr and McNair, 1964).

II. PATIENT STUDY

A. Recruitment

Fifty patients at Winnipeg and fifty patients at Oklahoma will receive neuropsychological testing. All patients will receive quality of life testing.

B. Testing

1. Baseline

- a. Neuropsychological Testing
 - i. Modified Halstead-Reitan

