(3) Brain Age Quotient - For the purposes of power calculations, a difference of 3 in mean values for the 12 hours and 24 hours treatment groups would be considered clinically important.

NOTE: The average change in each of the above variables between baseline and the six month anniversary will be compared for the two treatment groups.

Clinical Rating:

(1) Clinical Global Rating - For the purposes of power calculations, a .25 difference in mean values for the 12 hour and 24 hour treatment groups would be considered clinically important.

(2) Change in Global Rating - For the purposes of power calculations, a .25 difference in mean values for the 12 hour and 24 hour treatment groups would be considered clinically important.

NOTE: The average change in the clinical global rating between baseline and the six month anniversary will be compared for the two treatment groups. It will be important to indicate clearly the distinction between the above two variables.

MMPI:

(1) Number of MMPI Scores Above 70 - The MMPI scores to be considered in this count include F, HS, D, HY, PD, PA, PT, SC, SI, and MA. For the purpose of power calculations, a .50 difference in mean values for the two treatment groups would be considered clinically important.

(2) Mean Score of Ten Scales - The ten scales to be considered in the construction of this variable are listed above. For power calculations, a difference of 1 would be considered clinically important.

(3) ES (Ego Strength) Scale - For power calculations, a difference of 2.5 would be considered clinically important.

NOTE: The average change in each of the above variables between baseline and the six month anniversary will be compared for the two treatment groups. If it is necessary to reduce the number of variables for consideration, the variables labeled number of MMPI scores above 70 may be omitted.

Sickness Impact Profile:

(1) Total Score - For power calculations, a difference of 0.2 standard deviation units in mean value would be considered important.

(2) Physical Dimension - This variable will be calculated as the sum of the ambulation, mobility, and body care and movement subscales of the SIP. For power calculations, a difference of 0.2 standard deviation units in mean value would be considered important.

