(3) Psychosocial Dimension - This variable will be calculated as the sum of the social interaction, communication, alternance behavior, and emotional behavior subscales of the SIP. For power calculations, a difference of 0.2 standard deviation units in mean value would be considered important.

NOTE: The average change in each of the above variables between baseline and the six month anniversary will be compared for the two treatment groups. If it is necessary to reduce the number of variables for consideration, the physical dimension and psychosocial dimension variables may be omitted.

Katz Adjustment Scale:

- (1) R1 (Social Obstreperous)
- (2) R1 (Acute Psychotism)
- (3) R1 (Withdrawal Depression)
- (4) R2
- (5) R4
- (6) Discrepancy Score

NOTE: For each of the above variables, a difference of 0.2 standard deviation units in mean value would be considered important for power calculations. The average change in each of the above variables between baseline and the six month anniversary will be compared for the two treatment groups. If it is necessary to reduce the number of variables for consideration, the discrepancy score may be omitted.

Profile of Mood States:

- (1) Total Mood Disturbance - For power calculations a difference of 0.2 standard deviation units in mean value would be considered important.

NOTE: The baseline value for this variable will be the average of the two administrations before randomization. If only one administration before randomization is available, that value will be considered the baseline value. Since the POMS is administered at baseline, 1, 2, 3, and 6 months, a multivariate analysis will be utilized comparing the two treatment groups with respect to their average response at these five time points. However, attention will be focused at a comparison of the linear trend over time for the two groups.

Home Visit Behavior Checklist:

- (1) Average of All Cluster Scores - For the purposes of power calculations, a difference of 0.2 standard deviation units in mean values for the two treatment groups would be considered important.

- (2) Average of Depression, Hostility, Anxiety, and Lethargy Scores - For the purposes of power calculations, a difference of 0.2 standard deviation units in mean values of the two treatment groups would be considered important.

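### The attached NOTT minutes compare unadjusted change from baseline; adjusting for the baseline value would be more precise at no data cost, and the 0.2 SD target for SIP and KAS needs its SD named

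*Protocol*

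**What the plan says.** The protocol attaches the minutes of a NOTT subcommittee meeting of November 1978. They choose variables for deciding how long NOTT follow-up should run and say how the 12 hour and 24 hour groups will be compared.

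- **Change from baseline to six months.** The NOTEs under Halstead-Reitan Battery, MMPI, Sickness Impact Profile and Katz Adjustment Scale each state: "The average change in each of the above variables between baseline and the six month anniversary will be compared for the two treatment groups". The NOTE under Clinical Rating says: "The average change in the clinical global rating between baseline and the six month anniversary will be compared for the two treatment groups". No baseline covariate is mentioned.
- **Trend over time.** The Rennick Repeatable Battery, the POMS and the Home Visit Behavior Checklist get a multivariate analysis over five or six time points, with attention on the linear trend.
- **Important differences.** Halstead-Reitan, clinical rating and MMPI have absolute values (for example .10, .05, 3, .25). For SIP and KAS, "a difference of 0.2 standard deviation units in mean value would be considered important", with no statement of which standard deviation is meant.
- **Power.** The closing paragraph asks for new sample-size calculations using the standard deviations from accumulated data, and for conditional power.

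The Background section gives the reliability figures. For the SIP, "Test-retest reliability coefficients for the overall score are on the order of .90". For the KAS-R, "the median internal reliability for the five scales was found to be .725", and other studies "show similar high test-retest and internal consistency reliabilities", without a retest figure. For the POMS, "Stability coefficients ranged from .65 to .74 for a 20 day test-retest interval and from .43 to .52 for a six-week interval".

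**The concern.** In a randomised comparison, subtracting the whole baseline value removes too much whenever the baseline to follow-up correlation is below 1. The change score then carries baseline noise that a regression adjustment would leave out. The data needed for the adjustment are already collected.

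There is a second consequence. With equal SDs, a chance baseline difference d between groups shifts the change comparison by about (1−r)d in the opposite direction. The minutes ask for a comparability check on selected demographic variables only, so such an imbalance in the outcome itself is neither looked for nor adjusted.

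What is at stake is the precision of the results, and the sample-size and power figures, put before the Advisory Board when it decides on NOTT follow-up. For SIP and KAS those figures also depend on which SD the 0.2 refers to.

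**Working it through.** The minutes give no sample size, alpha or power for these comparisons, so there is no figure of theirs to reproduce.

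**Inputs**
- r = .90 for the SIP overall score (Background, SIP). It is a retest reliability with no interval given.
- r = 0.7 and r = 0.5 are assumptions, used to show a range.
- Important difference 0.2 SD (minutes, SIP and KAS), read first as 0.2 of the score's own between-patient SD.
- Assumed, because not stated: two-sided alpha 0.05, 80% power, 1:1 allocation, equal SDs at baseline and six months.

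**Variance per patient, in units of the score variance**
- Change score: 2(1−r)
- Six-month value adjusted for baseline: 1−r²
- Ratio, adjusted to change: (1−r²) / [2(1−r)] = (1+r)/2

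**Sample size per arm**

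n = 2 × (1.960 + 0.842)² × variance / 0.2² = 392.5 × variance, rounded up.

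**Power of the change comparison at the adjusted n**

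Φ(2.80 × √[(1+r)/2] − 1.96)

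| r | change variance | adjusted variance | ratio | n, change | n, adjusted | power on change at adjusted n |
|---|---|---|---|---|---|---|
| .90 (SIP) | 0.20 | 0.19 | 0.95 | 79 | 75 | 78% |
| 0.7 (assumed) | 0.60 | 0.51 | 0.85 | 236 | 201 | 73% |
| 0.5 (assumed) | 1.00 | 0.75 | 0.75 | 393 | 295 | 68% |

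The variance saving is therefore 5%, 15% and 25%.

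**Which SD does 0.2 refer to?** Take a change comparison of the SIP at r = .90.
- 0.2 of the score SD: n = 392.5 × 0.20 = 78.5, so 79 per arm.
- 0.2 of the SD of change: that SD is √0.20 = 0.447 score SDs, so the target is 0.2 × 0.447 = 0.089 score SDs. Then n = 2 × (2.802)² × 0.20 / (0.089)², which reduces to 392.5, so 393 per arm.

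The two readings differ by a factor of 1/0.20 = 5. At r = 0.5 they coincide, because the SD of change then equals the score SD.

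**Outcomes covered.** Three Halstead-Reitan variables, the clinical global rating, three MMPI, three SIP and six KAS variables: 3 + 1 + 3 + 3 + 6 = 16 of the 22 numbered variables.

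**The case against.** The strongest reply is that nothing here is an error. Mean change is unbiased under randomisation, and a plan to compare average change does not strictly exclude a baseline covariate. With baseline in the model, analysing change or the six-month value gives the same treatment estimate. The adjusted analysis is never worse only in large samples, since it spends a degree of freedom. The minutes serve a NOTT decision, and the IPPB part of the protocol fixes no between-group test. All of this stands. It makes the point a free improvement in precision and limits it to the NOTT analysis.

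Some stronger readings are tempting but not supported:

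- **A loss of 24% to 28.5%, from stabilities of .43 to .52.** Those figures belong to the POMS over six weeks, and the POMS is analysed by linear trend. They cannot be carried over to SIP or KAS. They do show that stability can fall with time, so a six-month correlation below a short-term retest value is plausible, but the documents give none. The KAS-R .725 is an internal reliability and is no substitute.
- **Power figures built on a wrong SD.** For a comparison of change, the SD of change is the right one. The Halstead-Reitan, clinical rating and MMPI differences are absolute, and under randomisation the expected difference in mean change equals that in mean six-month value. Only the 0.2 SD definition for SIP and KAS is open.
- **Nearly all outcomes affected.** Three instruments use trend analyses instead.

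**Conclusion.** The point holds as one of efficiency. For the Halstead-Reitan, clinical global rating, MMPI, SIP and KAS outcomes, unadjusted change is less precise than a baseline-adjusted comparison by the factor (1+r)/2. The only gain supported by a figure in the document is about 5%, for the SIP overall score at r = .90 (79 against 75 per arm). The 15% and 25% figures rest on assumed six-month correlations of 0.7 and 0.5.

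The undefined 0.2 SD for SIP and KAS can matter more: 79 or 393 per arm for a change comparison at r = .90. The sample sizes assume two-sided 0.05, 80% power, 1:1 allocation and equal SDs at the two visits.

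A reader might infer that the treatment comparison is biased, or that this is IPPB's primary analysis. Neither follows: change is unbiased under randomisation, and the minutes concern the 12 hour versus 24 hour NOTT comparison and the length of its follow-up.

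**What to change.** In the NOTEs for Halstead-Reitan, Clinical Rating, MMPI, SIP and KAS, state that the six-month value (or, equivalently, the change) will be compared between the two groups by analysis of covariance with the baseline value of the same variable as covariate. This point requires no further covariate. Leave out the Change in Global Rating variable if it is a direct rating of change with no baseline value.

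Use the residual SD of that model in the sample-size and power calculations requested at the end of the minutes.

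For SIP and KAS, state that the 0.2 SD important difference is in units of the baseline between-patient SD.

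The cost is wording and one degree of freedom per comparison. No new data are needed.
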